## **Abstract**

### *Background*

Post-operative rehabilitation is essential to optimize outcomes following orthopaedic surgeries. Lack of patient compliance to this prescribed rehabilitation therapy has been reported to be as high as 65%. This lack of rehabilitation compliance effects patients by prolonging pain and dysfunction and diminishing quality of life and acts as a strain on the healthcare system by increasing the overall burden of care, including increased duration of rehabilitation, increased rates of readmission, and re-operation.

### *Purpose*

The purpose of this pilot study is to ascertain if home-based therapy with monitoring via telemedicine can overcome barriers to compliance and improve rehabilitation.

### *Methods*

Sixty patients following total knee arthroplasty will be monitored for up to 10 weeks during their outpatient physical therapy course. For the control group, 30 of these patients will undergo two to three weekly sessions with a physical therapist supplemented by unmonitored home-based exercises. The second group of 30 patients will fulfill their rehabilitation course with one to three sessions per week with a physical therapist and will use the interACTION home rehabilitation monitoring program to supplement these sessions. The patients in the interACTION group will use the device for the first two weeks of their rehabilitation in the clinic in order to become familiar with the device before home use. After the first two weeks the patient will be asked to take the device home and reduce their weekly outpatient visits by one visit per week. However, if the physical therapist feels it is best for the patient to deviate from the protocol, this is allowed. At the end of the 10-week rehabilitation course, rehabilitation compliance, costs, and patient outcomes will be analyzed for differences between the two groups.

### *Significance*

If home-based therapy is successful, post-operative patients in the future would be allowed to perform guided rehabilitation therapy at home, and physicians would be able to monitor patients' rehabilitation progress without the limiting factor of patients being present onsite or performing the exercises incorrectly, potentially improving patient outcomes and lowering healthcare costs and expenditures.

## Background

Adequate rehabilitation following total knee arthroplasty (TKA) is crucial to optimize patient function and quality of life. Attaining adequate strength and range of motion is essential to regain the function of the knee and permit patients to resume their regular activities after surgery. Despite acknowledgement of the importance of post-operative rehabilitation after TKA, the current system is far from perfect. First, patients are expected to perform their rehabilitation program once or twice a day following surgery, but traditional rehabilitation protocols generally include only one to three sessions of outpatient physical therapy per week. As a result, the patient is left to perform exercises unmonitored for the majority of their recovery period. Second, barriers to rehabilitation are a concern for patients, including limited mobility/access and growing copay expenses. Lastly, the fragmented nature of the physical therapy landscape does not provide the physician or patient with a guarantee of a standardized, proven course of rehabilitation. This also makes accurate and meaningful communication between the physical therapist and physician a difficult task.

Altogether, these difficulties strain the optimal delivery of rehabilitation following TKA. Overall compliance to a complete rehabilitation program under the current standard of care approach to rehabilitation has been shown to be as low as 35% (Sluijs, Phys Ther, 1993).

Non-compliance, defined as incomplete or incorrect execution of prescribed treatments, represents significant waste in healthcare and negatively affects outcomes leading to prolonged pain, greater activity limitations and participation restrictions, a longer duration of recovery, poorer quality of life, and the potential for increased hospital readmissions and additional surgical interventions (Martin, 2005). Use of telemedicine to monitor patients has overcome barriers to compliance and reduced costs in other fields of medicine (Elkjaer, 2012). Early attempts to implement telerehabilitation have demonstrated a strong potential for the success of this approach in improving compliance (Russell, 2010). However, effective, scalable monitoring of prescribed exercises is currently limited by lack of portable, accurate, precise, interactive, and cost-effective tools. To date, remote rehabilitation or home exercise programs for rehabilitation after surgery or injury lack adequate supervision, patient motivation, patient-therapist communication, and personalized treatment plans.

Physical therapists can promote compliance in conventional rehabilitation by tracking patient adherence using log books, existing mobile apps, or activity monitors. However, log books rely on patients for accurate data entry and provide no means for communication or corrective feedback, existing mobile apps cannot track joint motion or provide corrective feedback, and activity monitors do not measure joint-specific function (quantity and quality of motion). Thus, current tools fail to quantify exercise over time in or out of the clinical setting.

InterACTION is a joint motion monitoring and training tool consisting of a wearable, portable motion capture device and a web-based software application for recording

and transmitting data. Sensors, placed on either side of a joint, collect joint motion and position data. Data is stored on a Bluetooth paired tablet. Motion data collected by interACTION is analyzed and displayed in a customizable, joint-specific manner in patient and therapist modes. The patient uses the system as often as indicated by their physical therapist to learn about the prescribed exercises, follow a personalized exercise program, demonstrate adherence to the treatment plan, and communicate problems with their physical therapist and receive interactive feedback. Patients also have the ability to view their rehabilitation progress.

A web-accessible, password-protected portal allows a local or remote physical therapist to monitor the patient's progress. Physical therapists have access to the data to analyze patient progress and compliance and review computer-generated alerts. Capabilities in the clinician portal include assessment of patient data during exercises and activities of daily living (ADLs), weekly progress reports by reviewing changes in important variables (i.e. range of motion, pain, patient-reported activity, participation, quality of life). The ability to monitor progress ensures the patient's compliance to the treatment program and allows clinicians to update the patient's exercise regimen as needed.

Use of the interACTION system has the potential to allow physical therapists to improve patient-oriented outcomes, streamline utilization of clinical resources, and provide care more efficiently for a larger number of patients. In turn, patients will be more confident and compliant with performance of their prescribed exercise program and will receive feedback on their recovery progress. However, research is needed to demonstrate these hypothesized benefits of the interACTION system.

## **Significance**

The interACTION telerehabilitation system provides flexibility and potential application at all stages of patient care, with easy implementation for patients at both the lower levels of the functional spectrum (e.g. immediately after joint surgery), as well as higher functioning individuals (e.g. >6 months post-op, athletes with persistent joint pain). The quality of care will improve as the therapist-patient relationship is strengthened by (i) providing valuable information about the patient's daily progress, (ii) improving compliance with the prescribed exercises, and (iii) facilitating communication/feedback between patient and physical therapist. By including physical therapists' guidance through the online activity manager and direct feedback, the patient will gain confidence that they are on the proper course for recovery. The physical therapist can monitor the progress of their patients to ensure joint function is improving and increase the patient's motivation and compliance to the prescribed therapy.

## **Methods**

For this randomized treatment study, we will recruit 60 patients that have undergone total knee arthroplasty (TKA) that are being referred for post-operative outpatient physical therapy. After obtaining informed consent, and upon successful

screening/recruitment, subjects will be randomly assigned to one of two groups:

1. Control Group: Rehabilitation performed by a physical therapist and supplemented with a home exercise program for a maximum of ten weeks. Therapy will consist of two to three visits per week as prescribed by the physical therapist and based on the best interest of the patient. Patients will record their performance of the prescribed home exercise programs on a paper-based exercise log on a daily basis.
2. InterACTION Intervention Group: Rehabilitation performed by a physical therapist and supplemented by use of interACTION for a maximum of ten weeks. This will include two to three visits per week for two weeks in which the patient will use interACTION during routine outpatient physical therapy sessions to familiarize them with the system. After two weeks, the patient will be issued an interACTION device for home use that will guide them through their exercise program. At this point subjects in the interACTION group should continue to return to the outpatient rehabilitation facility, but reduce their weekly routine visit with their physical therapist by one during the next eight weeks of recovery, while concurrently using interACTION at home. Patients who attended two visits per week for the first two weeks should subsequently attend one visit per week. Patients who attended three visits per week for the first two weeks will subsequently attend one to two visits per week. However, if the physical therapist feels it to be in the best interest of the patient to deviate from the protocol, this is allowed.

*Note: InterACTION is currently under development, not a commercial application. The 3rd Party Developer was OpenArc, LLC ([name]). The mobile application is currently supported on a Nexus tablet with Android operating system (specifically lollipop and kitkat versions). The mobile application and the kinematic sensors will be provided to the participant, the participants will NOT use a personal device.*

Rehabilitation Compliance will be evaluated by the study team through the use of home exercise logs and interACTION reports. Logs will be reviewed at the follow-up visits with the research team. Outcome measures will be collected at baseline, 5 weeks (+/- 7 days) after enrollment, and upon discharge or a maximum of 10 weeks (+/- 7 days) after enrollment.

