#### *Recruitment Methods*

Recruitment will be primarily done through UPP/CMI Orthopaedic Surgery clinics, which routinely care for patients that have undergone TKA. Patients will be identified through physicians who will be the primary medical provider in their perioperative care. Prior to the patient's first outpatient physical therapy visit, the study's research coordinator or research assistant will screen these patients, using the provided screening form, for inclusion/exclusion criteria and enroll/randomize those who meet the study's parameters. Subjects will not be recruited from skilled nursing facilities.

Recruitment flyers for the study will be made available at Orthopaedic Clinics and also at the Physical Therapist Outpatient Clinics. The flyer will be used to give potential patients information about the study and to enable them to contact us if they would like to participate. Potential patients may also be given flyers if they desire, so that they may have the contact information for the study in the event that the potential patient has any questions or concerns regarding the study.

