#### *Inclusion criteria*

Males and females between 40 and 80 years of age that have undergone primary unilateral TKA who have been referred for post-operative outpatient physical therapy will be eligible to participate in this study. Additionally, eligible subjects also need to be able to perform pre-defined exercises that they would normally

perform in a physical rehabilitation program.

The Physical therapists that will be asked to complete the Clinician Survey must have a patient participating in the study to be considered eligible.

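### Time since surgery is neither limited nor adjusted for, so readings timed from enrolment carry avoidable noise, most of all in the functional tests

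*Combined protocol and SAP*

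**What the plan says.** All references are to the combined protocol and SAP.

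- **Visit clock.** Methods: "Outcome measures will be collected at baseline, 5 weeks (+/- 7 days) after enrollment", and the last reading comes "upon discharge or a maximum of 10 weeks (+/- 7 days) after enrollment".
- **Enrolment and randomisation.** Recruitment Methods: "Prior to the patient's first outpatient physical therapy visit, the study's research coordinator or research assistant will screen these patients" and "enroll/randomize those who meet the study's parameters". No maximum gap between enrolment and the first therapy visit is given.
- **Eligibility.** Inclusion criteria: patients who "have undergone primary unilateral TKA who have been referred for post-operative outpatient physical therapy will be eligible". The inclusion and exclusion criteria cover age, BMI, comorbidity, and ability to exercise and to use the feedback. They set no minimum or maximum time since surgery.
- **Device schedule.** Methods: use in clinic comes first, then "After two weeks, the patient will be issued an interACTION device for home use", followed by eight weeks of home use. This schedule starts with outpatient therapy, not with enrolment.
- **Final analysis.** The Abstract's Methods paragraph places the analysis at the end of a ten-week rehabilitation course. The main Methods section uses discharge or ten weeks from enrolment.
- **Analysis.** Outcomes schedules the functional tests at the 5- and 10-week visits only. Statistical Analysis compares their averaged z-scores by a two-sample t-test. It uses repeated measures ANOVA for ADLS and flexion ROM, and t-tests or Wilcoxon tests for outcomes that are not normal throughout. It names no covariate, and no stratified randomisation is described.

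**The concern.** Function, motion and pain can be expected to change with time after knee arthroplasty. Two patients both read five weeks after enrolment can be at different points of that course if they were enrolled at different intervals after surgery. The plan neither restricts that interval nor uses it in the analysis. The resulting spread goes into the error term and, with 30 per arm, can by chance leave one arm further along in recovery than the other.

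ADLS, ROM, pain and VR-12 have a baseline reading that can absorb part of this. The functional tests have none, so their 5- and 10-week comparison carries all of it.

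A related matter is how the 5-week contrast is described. The visit clock and the device clock have different origins, so the amount of home use behind that reading varies between patients and is not stated.

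**Working it through.** **The plan's own figure.** There is none to reproduce. The document gives 60 patients (30 per arm) and a 0.05 significance level, but no effect size, SD or power. The size can only be shown over assumed values.

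**Inputs.** From the document: 30 per arm; alpha 0.05 (taken as two-sided, since sidedness is not stated); a window of ±1 week; two weeks in clinic; eight weeks at home; a ten-week maximum course. Assumed: recovery slope *b* of 0.05 to 0.2 SD per week; SD of weeks since surgery *s* of 1 to 3 weeks; gap *L* from enrolment to first therapy visit of 0 to 3 weeks.

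**Step 1: reference effect.** The difference detectable with 80% power is (1.960 + 0.842) × √(2/30) = 0.72 SD, where 1 SD is the spread among patients at the same time since surgery.

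**Step 2: extra variance.** With a linear slope, the SD in an unadjusted comparison is √(1 + (b·s)²). Power for the same 0.72 SD difference is then:

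| b (SD/week) | s = 1 week | s = 2 weeks | s = 3 weeks |
|---|---|---|---|
| 0.05 | SD 1.001, 79.9% | SD 1.005, 79.6% | SD 1.011, 79.1% |
| 0.1 | SD 1.005, 79.6% | SD 1.020, 78.4% | SD 1.044, 76.5% |
| 0.2 | SD 1.020, 78.4% | SD 1.077, 73.9% | SD 1.166, 67.1% |

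**Step 3: chance imbalance.** The standard error of the difference between arms in mean weeks since surgery is s × √(2/30), that is 0.26, 0.52 and 0.77 weeks for s = 1, 2 and 3. The 95% ranges are ±0.51, ±1.01 and ±1.52 weeks. Multiplied by the slope, the shift in the arm difference at the edge of that range runs from 0.05 × 0.51 = 0.03 SD to 0.2 × 1.52 = 0.30 SD. This is the same effect as in step 2 seen another way; the two are not additive.

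**Step 4: home use behind each reading.** Home weeks at a visit = visit week ± 1 − 2 − L, bounded by 0 and 8. Therapy weeks by a full-term final visit = 10 ± 1 − L, capped at the ten-week maximum.

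| L (weeks) | Home weeks at 5-week visit | Home weeks at 10-week visit | Therapy weeks at full-term final visit |
|---|---|---|---|
| 0 | 2–4 | 7–8 | 9–10 |
| 1 | 1–3 | 6–8 | 8–10 |
| 2 | 0–2 | 5–7 | 7–9 |
| 3 | 0–1 | 4–6 | 6–8 |

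With no gap at all, the visit window alone gives 2 to 4 weeks of home use at the 5-week reading.

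**The case against.** The strongest reply is that the effect may be small. Patients are identified through the physicians giving their perioperative care, are referred for post-operative therapy, and are enrolled before its first visit. That should keep most of them within a fairly narrow interval after surgery. At slopes of 0.05 to 0.1 SD per week the power loss is under four points, and the 67% figure needs the largest slope and the largest spread together. Baseline readings and repeated measures ANOVA already take up part of the spread for ADLS and flexion ROM. All of this stands. It does not help the functional tests, and it does not make an unused, readily obtained covariate a good choice.

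A reader might also infer more than the documents support:

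- **Bias between arms.** Time since surgery is fixed before randomisation and the enrolment clock is common to both arms, so the expected difference is zero. The discharge option is a separate matter: discharge follows randomisation, and its timing could differ by arm. That is a reason to settle the definition of the final reading.
- **A 5-week reading that cannot test home monitoring.** Zero home use requires a gap of about two weeks or more, with an early visit when the gap is two weeks. No gap is given, and recruitment just before the first visit would fit a gap of days.
- **Weeks of therapy left unassessed.** This needs the same assumed gap and a patient who goes the full term. Anyone discharged earlier may be read at discharge.
- **Enrolment of patients long after surgery.** The mention in Significance of "higher functioning individuals (e.g. >6 months post-op" describes possible uses of the system, not this trial's eligibility.
- **A need to restart the visit clock at first therapy.** That event follows randomisation, could differ by arm, and would leave a patient who never starts therapy without a schedule.

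**Conclusion.** The point holds as one of precision. The plan lets time since surgery vary without a stated limit, times readings from enrolment, and analyses them without adjustment. The cost is noise and chance imbalance, greatest for the functional z-score.

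The size cannot be fixed from the document. Under the assumed slopes and spreads, a comparison with nominal 80% power has between 67% and 80%, and most of the assumed range lies above 76%. These figures rest on a linear slope common to both arms and a normal approximation. For outcomes with a baseline they overstate the loss to the extent that the baseline is used.

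The wording on home exposure at 5 weeks and on the timing of the final reading needs clarifying, but neither is shown to invalidate a comparison.

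**What to change.** 1. Record the surgery date for every patient.
2. In Statistical Analysis, replace the unadjusted comparisons of ADLS, ROM, pain, VR-12 and the functional z-score with a linear model (ANCOVA, or a mixed model for repeated readings). Adjust for days from surgery to randomisation, and for the baseline score where one exists. The covariate is known before randomisation, so adjusting for it is safe.
3. Keep enrolment/randomisation as the visit clock. Record the dates of the first therapy visit and of device issue.
4. Reconcile the Abstract and the main Methods section on when the final reading falls: at discharge, ten weeks after enrolment, or at the end of the ten-week course.
5. Describe the 5-week contrast as the two-week clinic run-in plus at most about 2 to 4 weeks of home use, less any gap from enrolment to first therapy visit.

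**Cost.** One surgery date and two further dates per patient, one degree of freedom for the new covariate, and replacement of some t-tests and Wilcoxon tests, which can stay as sensitivity analyses. No visits are added. If the slope is close to linear, adjustment returns power to nearly 80%, a gain of 0 to 13 points over the range shown. Statistical Analysis is written in the past tense; if the data have already been analysed, the adjusted results should be labelled as added afterwards.

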### *Outcomes*

- Range of motion—Active and passive range of motion (ROM) will be measured with a standard goniometer while the patient lies in the supine position. Extension and flexion of each knee will be measured. Extension will be measured passively with a quad set and actively during a straight leg raise. The range of extension and flexion will be expressed as the difference between the involved and non-involved knees.
- Numeric Pain Rating Scale—Subjects will be asked to rate their level of pain currently and their level of worst & least pain in the past 24 hours on a scale from 0 (no pain) to 10 (worst pain imaginable).
- Activities of Daily Living Scale of the Knee Outcome Survey (ADLS)—The ADLS is a 14-item measure of symptoms and activity limitations for

individuals with a variety of knee impairments.

- Veterans RAND 12-Item Health Survey (VR-12)—The VR-12 is a 12-item patient-reported general measure of health-related quality of life that was adapted and developed from the RAND 36-Item Health Survey at the RAND Corporation and Medical Outcomes Study.
- Functional performance will also be tested in all patients. The following functional tests will be assessed at 5- and 10-week visits:
  - Six-minute Walk Test to assesses the subject's ability to walk community distances. The subject is asked to walk as far as possible in six minutes on a closed course with standing rest breaks as needed. The patient is free to use their preferred assistive device.
  - The Stair Climbing Test to test basic daily function in which a patient ascends and descends a standard flight of stairs as quickly and safely as possible, using their preferred gait pattern, assistive device, and hand rail.
  - The Timed Up and Go Test (TUG) in which the patient sits in a standard armed chair, rises, walks three meters, turns around, walks back to the chair and sits. Excessive time to complete the TUG can indicate mobility impairments and potential fall risks in elderly patients.
  - The Unilateral Balance Test in which the patient attempts to maintain single leg balance for up to two minutes, with the test ending when the patient loses balance enough to put the opposite foot on the ground.

Subjects will also undergo an interview to give a qualitative description of rehabilitation experience upon discharge from outpatient physical therapy or at the 10-week visit. This interview will entail an open-ended discussion with patients about their overall rehabilitation experiences, experiences with home exercises (either monitored or unmonitored), experiences with clinic-based workout sessions, and expenses incurred during the rehabilitation process.

Additionally, the physical therapists that are using the device with the study subjects will be interviewed to describe their experience with patient rehabilitation after surgery, and about their experience with the interACTION system.

The physical therapist will also be asked to complete the Clinician Survey, which will be administered by a research staff upon discharge of the patient, or a maximum of 10 weeks (+/- 7 days) after enrollment. All subjects participating in the study will be informed that their compliance will be evaluated by their physical therapist at this time of discharge, or a maximum of 10 weeks (+/- 7 days) after enrollment.

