#### *Statistical Analysis*

For the baseline data, continuous variables were compared with the two-sample t-test and categorical variables were compared with Fisher's exact test or a chi-square test.

For the primary outcome (value, ratio of ADLS to cost), the Wilcoxon rank sum test was used to compare between the Control Group and interACTION Group. P-Values below \* $p=0.05$  were considered statistically significant for all outcomes. For the remainder of the cost analyses parameters (weeks of physical therapy, number of physical therapy visits, and total cost), a two-sample t-test was used to compare between groups.

For other clinical outcomes data, if the distribution was normal at each time point, then a repeated measures ANOVA was used. A repeated measures ANOVA was used to compare difference between groups for the ADLS, Passive ROM (flexion), and Active ROM (flexion). Otherwise, if some time points had normal data and others did not then a two-sample t-test was used for normally distributed data and the Wilcoxon rank sum test was used for non-normally distributed data.

For the functional performance tests that were assessed at the 5- and 10-week visits, a z-score (or standard score) was used to calculate a cumulative score for the Six-minute Walk Test (distance in feet), Stair Climb Test (time divided by steps), TUG (time), and Surgical Unilateral Balance (time). The z scores are the average of the z scores for each of the functional tasks. On average, the z scores are close to zero, meaning that the overall individuals within the group, the scores for each subject are not different than the mean score across all subjects.

Differences between the cumulative z-scores were assessed using a two-sample t-test.

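### The procedure for passive knee extension contradicts itself: the reading is labelled passive but is taken with a quadriceps contraction

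*Combined protocol and SAP*

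**What the plan says.** Under Outcomes, the range-of-motion item opens with a commitment to two kinds of measurement: "Active and passive range of motion (ROM) will be measured with a standard goniometer while the patient lies in the supine position". For extension it then gives the manoeuvres: "Extension will be measured passively with a quad set and actively during a straight leg raise". The analysed quantity is a side-to-side contrast: "The range of extension and flexion will be expressed as the difference between the involved and non-involved knees".

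Under Statistical Analysis, the range-of-motion variables named for the repeated measures ANOVA are the flexion ones only: "A repeated measures ANOVA was used to compare difference between groups for the ADLS, Passive ROM (flexion), and Active ROM (flexion". Extension is not named. By implication it comes under the rule for the remaining clinical outcomes, by which "a two-sample t-test was used for normally distributed data and the Wilcoxon rank sum test was used for non-normally distributed data". The 0.05 threshold applies to it as well, since p-values below that level "were considered statistically significant for all outcomes". It is not the primary outcome: "For the primary outcome (value, ratio of ADLS to cost), the Wilcoxon rank sum test was used".

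**The concern.** A passive reading is one the patient does not produce by muscle effort. A quad set, as the term is normally used, is a voluntary isometric contraction of the quadriceps. A reading taken with a quad set therefore depends on effort, pain and quadriceps activation as well as on how far the joint will go, and an assessor cannot satisfy both halves of the phrase.

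What is at stake is the meaning of one declared outcome. The trial compares two ways of supporting an exercise programme, so quadriceps activation could plausibly differ between groups. A group difference in a contraction-dependent reading, reported as passive extension, would invite a conclusion about joint mobility that the measurement does not support.

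**Working it through.** The plan states no figure that depends on this sentence, so there is nothing to reproduce. The check sets the sections side by side.

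1. **What is promised.** Active and passive range of motion, for flexion and for extension: 2 × 2 = 4 kinds of reading.

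2. **What is described for extension.** Two manoeuvres: a quad set (labelled passive) and a straight leg raise (labelled active). Taking quad set in its usual sense, both require the patient to contract the quadriceps. Neither is clearly passive.

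3. **Whether another section resolves it.** Quad set is not defined. Nothing in Outcomes, in the rest of Methods or in Statistical Analysis describes a relaxed, supported or examiner-assisted extension reading, and no further instruction on measuring range of motion is given.

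4. **Whether the side-to-side expression removes the problem.** Let R be the relaxed extension angle of a knee and c the change that a quad set makes to it, with subscripts i (involved) and n (non-involved). The analysed value is

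   (R_i + c_i) − (R_n + c_n) = (R_i − R_n) + (c_i − c_n).

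   It equals the relaxed side-to-side difference only if c_i = c_n. Any part of the shift common to both knees cancels. An operated knee may respond differently to a contraction from the other knee, so full cancellation cannot be assumed. The documents give no value for c in either knee, so the remainder cannot be sized.

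5. **Where the reading goes.** Outcome measures are collected at baseline, 5 weeks, and discharge or at most 10 weeks. Extension would be compared between groups by the t-test or Wilcoxon rule and judged at 0.05. It does not enter the ratio of ADLS to cost, and the sentence at issue does not touch flexion.

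6. **Effect on the trial's design figures.** None. Correcting the instruction changes no sample size, significance level or visit.

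**The case against.** The strongest reply is that the phrase is loose shorthand. Quad set is undefined here, and the intention may have been a supported leg with a quad set added; the wording does not prove that every reading recorded as passive was made by contraction. This stands as a limit on what can be said about the actual readings. It does not rescue the instruction: a supported leg with a contraction added is still not a passive measurement, and an ambiguous procedure needs clarifying in any case.

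The second reply is that little depends on it. Extension is non-primary and unnamed in the analysis section, and both groups are measured under the same instruction, so no procedural bias between groups is shown. That is correct and bounds the impact. It does not answer the concern about what the variable measures.

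Three stronger readings are tempting, and the documents support none of them:

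- **A planned passive-versus-active comparison, or an extensor lag, has been lost.** Neither is defined. The plan forms differences between knees and compares groups. Moreover, the quad set and the straight leg raise remain distinct manoeuvres and are not shown to measure the same thing.
- **Assessors will divide between relaxed and contracted technique.** Nothing is said about the number of assessors, their training or their variation. If all used a quad set, the result would be a mislabelled variable without any mixed-technique error.
- **The error can be put in degrees.** That would need an assumed shift and an assumed mix of techniques, and would have to allow for the part that cancels between knees.

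**Conclusion.** The point holds in a limited form. The instruction for passive extension is internally inconsistent, and the plan describes no extension reading that would justify the label. The affected measure is one of the four kinds of range-of-motion reading. It is non-primary, but the instruction covers every patient at each visit where the reading is taken. The primary outcome and flexion are unaffected.

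The conclusion rests on one assumption from outside the text: that quad set carries its usual meaning of a voluntary quadriceps contraction. It is a matter of labelling and construct validity. A reader might go further and infer bias between the groups, or that the existing readings are worthless. Neither follows: the procedure is common to both groups, and a quad-set reading remains usable if it is named for what it is.

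**What to change.** Reword the extension sentence so that passive extension is read with the quadriceps relaxed, by the same method on both knees and at every visit. If a quad-set reading is also wanted, record it as a separate variable under an active label, alongside the straight leg raise.

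Statistical Analysis is written in the past tense, so readings may already exist. In that case, establish how they were taken. Those taken with a quad set should be relabelled as extension with quadriceps contraction, and no conclusion about passive extension should be drawn from them.

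The cost is one sentence of measurement instruction and, where data exist, a change of variable name. The goniometer, the supine position and the visits stay as they are. The downside is that a relaxed reading cannot be recovered for visits already completed, so passive extension may have to be reported as not measured.
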